6.3.3.9 ECG

A single 12-lead ECG will be obtained during Screening after the subject has been in a supine position for 10 to 15 minutes. The ECG should include measurements of ventricular rate, PR, QRS, QRS axis, QT, QTcb or QTcf, ST segment, T wave as well as an investigator assessment of whether the ECG is normal or abnormal (automated interpretations of ECG should not be used). Abnormal ECGs should be interpreted as "clinically significant (CS)" or "not clinically significant (NCS)" by the investigator.

6.3.3.10 Subject Self Evaluation

Subjects will be provided a PDC and will be asked to record the following the evening of study treatment through Day 6:

- Oral temperature and time taken (before 11:59 pm)
- General symptoms of feeling unwell
- Pain and itching at injection site
- Measure redness, swelling, bruising at injection site
- Medications taken

The completed PDC will be reviewed with the subject by the study staff at 8 -14 days post-dose phone call and next in-person visit.

The study staff will review the PDC for general symptoms (e.g. malaise, fatigue, headache, nausea, and myalgia/arthralgia), injection site reaction symptoms (e.g. pain, erythema and edema), medical events and medications.

Any PDC entry determined to meet the CTCAE criteria for a Grade 1 or higher adverse event should be documented as an adverse event unless deemed part of the subject's ongoing medical history. If the PDC entry does not meet the criteria of a Grade 1 or higher AE as per the CTCAE guidelines, clinical judgment can be used to determine whether the entry should be recorded as an AE and documented accordingly in the site's source. For cases where the PDC entry and final AE reporting (i.e. grading) do not agree, the reasoning should be recorded in the source documents.

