15 APPENDICES

15.1 APPENDIX A: PARTICIPANT DIARY CARD

Subject Diary HPV-301

Subject #:	
Injection Date:	

Note to Participant:

For questions or problems, please contact your Site Coordinator.

Name:	
Telephone: ()	
Email (optional):	

Participant Diary HPV-301 Version 1.0 - 10 May 2016

Temperature

Take your temperature orally around the same time each evening, using the thermometer provided and record it in the space provided. Also record the time at which you took your temperature. If you recently drank very hot or cold liquids, wait 15 minutes before taking your temperature.

Injection Site Symptoms

Pain and itching

Some people experience pain in the area where they were injected. Some people may also experience itching in the area where they were injected.

. By pain we mean that the place where you were injected hurts even when it isn't touched.

If you experience pain or itching at the injection site, use the following categories to describe how severe these symptoms were. If you don't experience one or more of these symptoms, mark the NONE box.

- Mild in I only had a little discomfort. I could still use my arm like always.
- Moderate ! I noticed the discomfort and didn't use my arm as much as usual.
- Severe ! I really noticed the discomfort. It kept me from doing something I wanted or had to do.

Redness, swelling, and bruising

Some people experience redness, swelling, or bruising in the area where they were injected. If you experience redness, swelling, or bruising, measure the area using the measuring tool you were provided, and record the measurement in the space provided.

To measure the area of redness, swelling, or bruising, do the following:

- Place the measuring tool over the area where you were injected, with the dot over the center of the area.
- Select the circle where the longest part of the area touches the line.
- If the area is in between two circles, select the larger circle.

For example, the area shown to the right measures 3 centimeters (cm) because it is touching the 3cm line.

General and Other Symptoms or Medications

If you have additional symptoms that are not listed, or if you sought medical care for any reason from a health care provider (e.g. doctor's office, emergency room), or if you took any medications, these should be listed in the spaces provided. Please designate any symptoms as Mild, Moderate, or Severe.

- Mild I only had minor discomfort. I went about my usual activities.

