- iii. Section 8.9 (Efficacy Analysis) has been revised to add a description regarding the Immunoscore analysis per Exploratory Objective 6.
- iv. Section 8.10 (Immunogenicity Analyses) has additional clarifying information regarding the evaluation of immune assays.
- v. Section 8.11.1 (Adverse Events) has been revised to clarify the use of start and stop dates of adverse events for analysis purposes.
- vi. Section 8.14 (Patient Reported Outcomes) has been revised to change the testing method from non-parametric or Miettinen and Nurminen to Wilcoxon rank-sum test or Pearson chi-square test/Fisher's exact test, which is appropriate for scales with multiple categories rather than only two categories.
- q. Section 9.4.2 (Pathology Adjudication Committee) now refers to the PAC charter, which has the most current information regarding the PAC review process.
- r. The Participant Diary Card is unchanged but has been removed from the Appendix since the Participant Diary Card is a separate document.
- 5. Additional minor grammatical and administrative changes have been made throughout the document for improvement of general readability.

INVESTIGATOR ACKNOWLEDGEMENT

I have read this Protocol and agree that it contains all necessary details for carrying out the study described. I understand that it must be reviewed by the Institutional Review Board or Independent Ethics Committee overseeing the conduct of the study and approved or given favorable opinion before implementation.

The signature of the Investigator below constitute his/her approval of this protocol and provide the necessary assurances that this study will be conducted according to the Declaration of Helsinki, ICH-GCP guidelines, local legal and regulatory requirements as well as to all stipulations of the protocol in both the clinical and administrative sections, including statements regarding confidentiality.

Investigator – Signature	Date (DD/MMM/YYYY)
Investigator – Printed Name	
Site Number:	
Site Name:	

TABLE OF CONTENTS

St	ımma	ry of Changes	3	
In	vestig	ator Acknowledgement	7	
Ta	able o	f Contents	8	
i	List	Of Abbreviations and definitions	13	
ii	Clin	ical Protocol Synopsis	15	
1	Intro	oduction		
	1.1	Background	24	
		1.1.1 HPV Infection, Cervical Intraepithelial Neoplasia and Cervical Cancer	24	
		1.1.2 VGX-3100	25	
		1.1.3 Electroporation	25	
		1.1.4 Selection of study design	26	
	1.2	Dose and Regimen Rationale	27	
	1.3	Risks/Benefit Assessment		

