2.3 SAFETY MONITORING PLAN

Although cervical HSIL is thought to require years to progress to cervical cancer, subjects in the Phase 2b study were followed closely throughout. HPV testing (Weeks 14 and 24), cytology (Week 14) and colposcopy (Week 24) were all mandatory during the observation period prior to obtaining tissue for determination of the primary histologic endpoint at Week 36. Investigators were also instructed to perform additional testing (including biopsy) if disease progression was suspected. These instances were infrequent as only 11 unscheduled biopsies were deemed necessary over the course of the Phase 2b study. In addition, the rate at which occult microinvasive cancer was discovered after 36 weeks was less frequent than what is reported in the literature [22]. Both observations would imply that the mandatory monitoring employed in the Phase 2b study was sufficient; however cervical disease will be monitored even more closely in this Phase 3 study. Colposcopy, cytology and HPV testing will be required at 8 to 14 week intervals throughout the observation period leading up to the primary endpoint 36 weeks after the first dose. Although less frequent monitoring may be adequate, the more frequent monitoring is designed to afford an even wider margin of safety and an opportunity to explore predictors of efficacy.

Safety monitoring will include:

• Local and systemic events for 7 days following each treatment as noted on a Participant Diary Card (PDC).

 All adverse events including SAEs, UADEs, and other unexpected AEs for the duration of the study;

In the Phase 2b study, the safety profile was carefully evaluated and treatment with VGX-3100 was well-tolerated based on observations through Week 88 in all subjects. The most common adverse events were administration-site reactions, which included pain, tenderness, erythema and swelling, and were generally mild and limited to a few days in duration. Only erythema showed a statistically higher incidence in VGX-3100 (78%) vs. placebo (57%) in the 7- and 28-day periods after a dose. One additional AE, sinusitis, was also statistically significantly increased over the course of the entire study period but resolved without sequelae in the VGX-3100 arm compared to the Placebo arm (10% vs. 0%).

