6.6 ASSESSMENT OF CLINICAL STUDY ADVERSE EVENTS

The injection site will be assessed by study personnel prior to and at least 30 minutes after each study treatment and at 2 to 4 weeks post study treatment visits. They will also be advised to record local and systemic AEs for 7 days on a PDC.

An adverse event assessment will be conducted at each visit during which subjects will be queried regarding the occurrence of any adverse events, concomitant medications new onset illness or disease, as well as contraceptive compliance. Subjects will be reminded to contact study personnel and immediately report any event that happens for the duration of the study. Unsolicited adverse events will be captured from the time of the informed consent to study discharge. These events will be recorded on the subject's CRF.

6.7 ASSESSMENT OF INJECTION SITE REACTIONS

When evaluating injection site reactions throughout the study, the investigator will be instructed to use the following grading scale:

Table 15. Grading Scale for Injection Site Reactions

Local Reaction to Injectable Product (Grade)	Mild(1)	Moderate(2)	Severe(3)	Potentially Life Threatening(4)
Pain	Does not interfere with activity	Repeated use of non- narcotic pain reliever >24 hours or interferes with activity	Any use of narcotic pain reliever or prevents daily activity***	Emergency room (ER) visit or hospitalization
Tenderness	Mild discomfort to touch	Discomfort with movement	Significant discomfort at rest	ER visit or hospitalization
Erythema/Redness*	2.5-5 cm	5.1-10 cm	>10 cm	Necrosis or exfoliative dermatitis
Induration/Swelling**	2.5-5 cm and does not interfere with activity	5.1-10 cm or interferes with activity	>10 cm or prevents daily activity	Necrosis

September 2007 "FDA Guidance for Industry—Toxicity Grading Scale for Healthy Adult and Adolescent Volunteers Enrolled in Preventive Vaccine Clinical Trials"

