7.3.1 ADVERSE EVENTS OF SPECIAL INTEREST

Adverse events of special interest (AESI) are the adverse events deemed related to VGX-3100/placebo delivered with CELLECTRA[™] 5PSP that require expedited communication from the Site to the Sponsor and meet any of the following criteria:

- Grade 3 or greater persistent administration site erythema, and/or induration recorded ≥ 2 hours immediately after Study Treatment
- Grade 4 or greater persistent administration site pain, tenderness recorded ≥ 2 hours immediately after Study Treatment
- Grade 3 or greater fever
- Grade 3 or greater systemic symptoms, including generalized pruritus

Sites will inform the Sponsor via method described in section 7.4.1 within 24 hours to discuss whether further dosing for the particular subject should continue.

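### The diary does not prompt for injection-site tenderness from the evening of dosing through Day 6, so mild tenderness is likely to be under-recorded against the reactions it does solicit

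*Protocol*

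**What the plan says.** - **Endpoint.** Secondary endpoint 1a (Section 3.3) is the incidence and severity of local and systemic events for 7 and 28 days after each treatment and over the whole study. Section 8.11.1 plans a separate summary of events within 7 days of any dose.
- **Source of the 7-day data.** The synopsis and Section 2.3 both name the Participant Diary Card as where local and systemic events are noted for 7 days after each treatment.
- **Diary content.** Section 6.3.3.10 runs the diary from the evening of treatment through Day 6. The local items are "Pain and itching at injection site" and "Measure redness, swelling, bruising at injection site". The symptoms staff are told to look for when they review it are, by example, pain, erythema and edema.
- **Diary wording.** The card printed in the appendix of the protocol text preceding version 4.0 says: "By pain we mean that the place where you were injected hurts even when it isn't touched". The version 4.0 Summary of Changes states: "The Participant Diary Card is unchanged but has been removed from the Appendix since the Participant Diary Card is a separate document". The version 5.0 change list names no diary change, and version 5.0 does not reproduce the card.
- **Grading.** Table 15 (Section 6.7) has a tenderness row separate from the pain row. Its Grade 1 is "Mild discomfort to touch".
- **Expectation.** On Phase 2b, Section 2.3 reports: "The most common adverse events were administration-site reactions, which included pain, tenderness, erythema and swelling".

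**The concern.** The protocol grades tenderness as its own reaction and expects it to be common, but the only instrument filled in daily during the 7-day window never names it. The card goes further: a woman whose arm hurts only when pressed, and who follows the instruction, should mark no pain. Her Grade 1 tenderness then has no box of its own and is steered out of the nearest one.

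At stake is the completeness of part of a secondary safety endpoint. In the 7-day table, tenderness would be largely volunteered while pain, itching, redness, swelling and bruising were asked about every evening. The rates would sit side by side without being comparable, and a low tenderness rate could be read as good tolerability. No later analysis plan can repair this, because an answer that was not asked for cannot be recovered.

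**Working it through.** The protocol states no figure to reproduce. The check sets the diary against Table 15 and then follows every route by which tenderness could be recorded.

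**1. Named prompts.** Inputs: daily pages for Day 0 to Day 6, so 7 days (Section 6.3.3.10 and the printed card), and 3 doses (Section 6.4). Diary days per woman = 7 × 3 = 21. Tenderness is named on 0 of 21. Pain, itching, redness, swelling and bruising are each named on 21 of 21. This counts named prompts for a woman who receives all three doses; it does not count cases captured or lost.

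**2. Where each tenderness grade would land on the card.**

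| Table 15 tenderness | Where it fits on the diary |
|---|---|
| Grade 1: touch only | Outside the card's definition of pain; other-symptoms field only |
| Grade 2: on movement | May be ticked as pain, since the card's moderate level is reduced use of the arm |
| Grade 3: at rest | Meets the card's definition of pain |
| Grade 4: emergency visit or hospitalization | The card asks about medical care sought and gives the emergency room as an example |

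Only Grade 1 is clearly excluded. Grades 2 and 3 may be classed as pain instead of being lost.

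**3. Routes over time after a dose.**

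| Time | Route | Tenderness named? |
|---|---|---|
| Day 0, at least 30 minutes after dosing | Staff, using Table 15 (Sections 6.6, 6.7) | Yes |
| Evening of Day 0 to Day 6 | Diary | No |
| Day 8-14 | Phone evaluation of injection-site reactions (Sections 6.2.2, 6.2.4, 6.2.7) | Not by name; by recall |
| Next site assessment | Staff, using Table 15 | Yes |

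The call falls 8 − 6 = 2 to 14 − 6 = 8 days after the last diary day. By nominal visit week, the next visit that assesses the site is 4 weeks after dose 1 (Week 4), 8 − 4 = 4 weeks after dose 2 (Week 8) and 15 − 12 = 3 weeks after dose 3 (Week 15). No scheduled staff assessment falls on Days 1 to 6.

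**Result.** What is missing is a named, same-day prompt for tenderness from the evening of dosing through Day 6. The gap matters most for Grade 1.

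**The case against.** The strongest reply is that tenderness has several other routes into the data. Staff assess the site before and at least 30 minutes after each dose and again at 2 to 4 weeks, with a scale that includes tenderness. The Day 8-14 call has its own injection-site evaluation, separate from diary review, and can lead to an office visit. The card covers unlisted complaints ("If you have additional symptoms that are not listed") and asks each day whether there were any. Adverse events are queried at every visit. All of this stands, and it rules out the tempting reading that tenderness goes unmeasured when it occurs. It does not close the gap, because none of these routes names tenderness at the time it would be felt on Days 1 to 6.

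A reader might also infer that the count of adverse events of special interest, and with it the study pause, is compromised. The documents do not support this. Section 7.3.1 requires "Grade 4 or greater persistent administration site pain, tenderness recorded" 2 hours or more after treatment, and Table 15 makes Grade 4 an emergency visit or hospitalization. The card's question on medical care would pick that up, and a hospitalization also falls under 24-hour serious-event reporting. No pause rule in Section 7.3.2 is driven by Grade 1 reactions.

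A third inference is that a treatment difference in tenderness will be shrunk. Section 2.3 says only erythema had a statistically higher incidence in Phase 2b in the 7- and 28-day periods (78% v 57%), and the protocol gives no tenderness rate by arm. There is no documented difference to shrink.

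Finally, the pain definition is known only from a superseded appendix. That caveat holds. The missing item does not depend on it, since the current Section 6.3.3.10 omits tenderness too.

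**Conclusion.** The point holds in a limited form. The diary behind the 7-day local events does not prompt for tenderness, and its pain definition excludes touch-only discomfort. Grade 1 tenderness on Days 0 to 6 is therefore likely to be under-recorded relative to the solicited reactions. The only size the documents support is the prompt count, 0 of 21 against 21 of 21. They give no tenderness incidence and no volunteering rate, so the number of missed cases cannot be estimated.

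The conclusion assumes that the card in use under version 5.0 still carries the printed wording and rows, and that reactions which are not prompted are reported less completely than those that are. It is an inexpensive improvement to one secondary safety endpoint and does not threaten the trial's safety oversight or its treatment comparison.

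**What to change.** 1. Add a tenderness row to each diary day, with severity wording matched to Table 15, so that touch-only discomfort has a box and the row is distinguishable from pain.
2. List tenderness among the diary items in Section 6.3.3.10.
3. For women who used the existing card, keep staff-graded tenderness as recorded. Do not relabel it as unsolicited. Footnote the 7-day local-reaction table to say that the diary did not solicit tenderness.

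The cost is one extra line per diary page, a re-issued and translated card, and 7-day tenderness results shown by diary version. Diary days already completed cannot be recovered. If dosing has finished, only the footnote remains.

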6.4 INJECTION AND ELECTROPORATION (EP)

Subjects will receive a 3-dose series of either 1 ml VGX-3100 or Placebo by IM injection in the deltoid (or anterolateral quadriceps muscle as an alternate option, if deltoid muscle is not possible or appropriate) followed immediately by EP with the CELLECTRA™ 5PSP. Study treatment must not be given within 2 cm of a tattoo, keloid or hypertrophic scar. If there is implanted metal, implanted device, within the same limb then use of the deltoid muscle on the same side of the body is excluded.

6.4.1 RISKS OF TREATMENT PROCEDURES

A summary of the potential risks of IM administration followed by EP with the CELLECTRA[™] 5PSP can be found in the VGX-3100 Investigator's Brochure.

6.4.2 MANAGEMENT OF ANXIETY AND PAIN DUE TO TREATMENT

Subjects may be offered topical anesthetic (e.g. EMLA or equivalent), to prevent significant discomfort from the treatment procedure. If a topical anesthetic is used, an approximately 1.5 cm diameter amount will be applied with occlusion to the site of injection ~30 minutes prior to treatment.

Subjects may be offered a mild sedative (e.g. 0.5-1 mg lorazepam), or equivalent, for anxiety related to the treatment procedure. Mild sedatives may be administered approximately 1 hour prior to treatment at Day 0, Weeks 4 and/or 12. Subjects who receive a mild sedative should not be allowed to operate a motor vehicle for 3-4 hours after receiving medication and should have arranged transportation to depart the study site.

Subjects may be offered an analgesic (e.g. ibuprofen, ketorolac) after injection/EP.

Subjects who are allergic to or have contraindications to EMLA, ibuprofen, ketorolac or a mild sedative may be offered a suitable alternative.

Medication taken for anxiety or pain management should be added to the concomitant medications.

6.5 ASSESSMENT OF LABORATORY ABNORMALITIES

Blood will be drawn for serum chemistry, hematology and serology assessments as well as urine pregnancy testing at Screening will be performed for inclusion into the study as listed in section 6.1.1.

6.6 ASSESSMENT OF CLINICAL STUDY ADVERSE EVENTS

The injection site will be assessed by study personnel prior to and at least 30 minutes after each study treatment and at 2 to 4 weeks post study treatment visits. They will also be advised to record local and systemic AEs for 7 days on a PDC.

An adverse event assessment will be conducted at each visit during which subjects will be queried regarding the occurrence of any adverse events, concomitant medications new onset illness or disease, as well as contraceptive compliance. Subjects will be reminded to contact study personnel and immediately report any event that happens for the duration of the study. Unsolicited adverse events will be captured from the time of the informed consent to study discharge. These events will be recorded on the subject's CRF.

6.7 ASSESSMENT OF INJECTION SITE REACTIONS

When evaluating injection site reactions throughout the study, the investigator will be instructed to use the following grading scale:

Table 15. Grading Scale for Injection Site Reactions

Local Reaction to Injectable Product (Grade)	Mild(1)	Moderate(2)	Severe(3)	Potentially Life Threatening(4)
Pain	Does not interfere with activity	Repeated use of non- narcotic pain reliever >24 hours or interferes with activity	Any use of narcotic pain reliever or prevents daily activity***	Emergency room (ER) visit or hospitalization
Tenderness	Mild discomfort to touch	Discomfort with movement	Significant discomfort at rest	ER visit or hospitalization
Erythema/Redness*	2.5-5 cm	5.1-10 cm	>10 cm	Necrosis or exfoliative dermatitis
Induration/Swelling**	2.5-5 cm and does not interfere with activity	5.1-10 cm or interferes with activity	>10 cm or prevents daily activity	Necrosis

September 2007 "FDA Guidance for Industry—Toxicity Grading Scale for Healthy Adult and Adolescent Volunteers Enrolled in Preventive Vaccine Clinical Trials"

6.8 ASSESSMENT OF PATIENT REPORTED OUTCOMES

To assess quality of life and related impacts on subjects, two previously-validated patient-reported outcomes (PRO) instruments will be provided to the subjects enrolled in US, Canada, Mexico, UK and Germany. The following two PRO questionnaires will be used:

- 1. Short Form Health Survey, **version 2** (**SF-36v2[™]**) (Optum, Inc.): generically measures functional health and well-being, for physical and mental health; consists of thirty-six items covering eight domains (Physical functioning, Role limitations due to physical problems, Bodily pain, General health, Vitality, Social functioning, Role limitations due to emotional problems, and Mental health) [26]
- 2. **EQ-5D-5L** (EuroQol Research Foundation): generically measures activities & general health status; consists of six items covering six domains (Mobility, Self-care, Usual activity, Pain/discomfort, Anxiety/depression, and Global health status) [27, 28]

Either one or both PRO instruments (refer to Section 6.2) will be provided to the subject who will be instructed to complete the questionnaire at the following time points:

- Day 0 (*before* the first study treatment)
- 8-14 days post dose 1
- Week 4 (after study treatment)
- 8-14 days post dose 2
- Week 12 (after study treatment)

^{*}In addition to grading the measured local reaction at the greatest single diameter, the measurement should be recorded as a continuous variable

^{**}Induration/Swelling should be evaluated and graded using the functional scale as well as the actual measurement
*** Sponsor defines daily as impact lasting > 24 hours

- 8-14 days post dose 3
- 8 -14 days post Week 28
- Week 36 (after biopsy or surgical excision)
- 8-14 days post Week 40
- Week 88

Administration of PRO instruments will be performed according to the validated procedure and guidelines of each respective instrument, except for some assessments for exploratory analyses. Additional instructions will be provided separately.

Additional questions related to the subject's quality of life following surgery or biopsy will be completed at the Week 40 phone call for subjects enrolled in USA, Canada, Mexico, UK and Germany.

